1.2. Study Schematic

Figure 1: Study Schematic

^{*}Standard of Care

Patients who participate in the OLE will continue to receive rodatristat ethyl for 6.5 years, until the Investigator or patient chooses to stop the IP, any stopping criteria in the Main Study are met, IP becomes commercially available, or the Sponsor stops the study for lack of efficacy or a safety signal (whichever preceding criteria comes first). In no case will a patient be allowed to exceed 10 years of exposure unless the product is approved for a chronic indication.

Abbreviations: BID = twice daily; IP = investigational product

DocuSign Envelope ID: A0018C3E-C7AD-4578-9E8C-9E8AC2E9E766

Clinical Study Protocol Altavant Sciences GmbH

Protocol RVT-1201-2002 Effective: 19JAN2022

Schedule of Assessments - Main Study 1.3.

		:			E				
	Screening	Baseline			I reatment	snt			Follow-Up
Visit No.	Visit 1	Visit 2	Visit 3	Visit 4	Visit 5	Visit 6	Visit 7	Visit 8	Visit 9
Study Week ¹	-4 Wks ²	D1	Wk 2 (D14)	Wk 4	Wk 8 (D56)	Wk 12	Wk 18 (D126)	Wk 24	Wk 28
(Days)	(D-28 to D-1)	Clinic	Telemed/	(D28)	Clinic or	(D84)	Clinic or Home	(D168)	(D196)
	Clinic		Phone Call	Clinic	Home	Clinic		Clinic	FU ^{3/} ET ^{3,4}
									Clinic or Home
Screening/ Demography/ Baseline									
Informed Consent	×								
Inclusion/Exclusion Criteria	×	X							
Demographics	X								
Height/Weight/BMI	X	Xş		X^5	Xş	X ₅		ςX	X ₂
Medical History Including Cardiac and Pulmonary History/Current Conditions ⁶	X	X							
PAH Medication History ⁷	X	X							
Pulmonary Function Tests (PFTs) (unless completed in last 24 weeks)	X								
FSH ⁸	X								
Urinary Screen for Drugs of Abuse	X								
Register Patient in IRT Screening/Randomization	X	X							
Treatment									
Concomitant Medications	X	X	X	X	X	X	X	X	X
Dispensing IP via IRT		×		×		×			
Administer Rodatristat Ethyl or Placebo ⁹		X	X	X	X	X	X		
Morning Dose Taken in Clinic with Food ⁹		X		X					
Investigational Product Compliance/ Accountability				X		X	X	X	
Safety/Tolerability Assessments									
Adverse Events ¹⁰					$\uparrow \times \to$				
Pregnancy Test (Serum/urine)11	X	X		X	X	X		X	X
Physical Examination	X	X		X		X		×	

DocuSign Envelope ID: A0018C3E-C7AD-4578-9E8C-9E8AC2E9E766

Clinical Study Protocol Altavant Sciences GmbH

Protocol RVT-1201-2002 Effective: 19JAN2022

	Screening	Baseline			Treatment	ent			Follow-Up
Visit No.	Visit 1	Visit 2	Visit 3	Visit 4	Visit 5	Visit 6	Visit 7	Visit 8	Visit 9
Study Week¹ (Days)	-4 Wks² (D-28 to D-1) Clinic	D1 Clinic	Wk 2 (D14) Telemed/ Phone Call	Wk 4 (D28) Clinic	Wk 8 (D56) Clinic or Home	Wk 12 (D84) Clinic	Wk 18 (D126) Clinic or Home	Wk 24 (D168) Clinic	Wk 28 (D196) FU ^{3/} ET ^{3,4} Clinic or Home
Vital Signs (BP, HR, RR, temp, oxygen saturation)	X	X		×	×	×	X	X	X
12-Lead ECG ¹²	X	X		×	×	×	×	X	×
Laboratory – Hematology, Coagulation ¹³ , Chemistry, urinalysis,	X	X		×	×	×	×	X	×
Columbia-Suicide Severity Rating Scale (C-SSRS)	X	X		×		×	×	X	X
Hospital Anxiety and Depression Scale (HADS)	X	X		×		×	×	X	X
Quick Inventory of Depressive Symptoms (QIDS-C)	X	X		×		×	×	X	X
Efficacy-Related Assessments									
5 TWM5	X	X		X		X		X	
Right Heart Catheterization (RHC) ¹⁴	X							X	X^{14}
Echocardiography ¹⁵	X					X		X	
WHO FC	X	X		X		X		X	
Plasma NT-proBNP level		×		×		×		×	
PAH Symptoms and Impact Questionnaire (PAH-SYMPACT)		X				×		X	
Actigraphy ¹⁶					\	$X \rightarrow$			
Pharmacokinetics									
Rodatristat PK Sampling ¹⁷		X		X		X		X	
Selexipag PK sampling ¹⁸		X		×					
Pharmacodynamics		Α		Þ		Þ		Α	
Ullile J-HIAA		< >		< >		< >		< >	
Plasma 5-HIAA ¹⁷		X		×		×		X	
Other									
Optional Blood for Future Research Sample		X						X	
Pharmacogenetic Samples		X						X	

Clinical Study Protocol Altavant Sciences GmbH

Visits at Week 2 (Telemed/Phone Call) and Week 4 (clinic visit) can occur within +/-2 days from the randomization date; Visits at Weeks 8 (Telemed/Phone call), 12 (clinic), 18 (clinic or home visit), 24 and 28/Follow Up (clinic) can occur within +/-5 days from the randomization date.

² Screening may be broken up into more than 1 visit, if necessary. Once all screening procedures are complete and the Investigator determines that the patient is eligible, the site must upload/send the required supporting documentation for approval by the Sponsor.

withdraw consent will continue to be followed for vital status from public records such as government vital statistics or obituaries, as allowed by local law, or periodic contact Patients who early terminate from the IP should be asked to return for visits as scheduled for ongoing assessments through the Week 28 Visit. Patients who withdraw consent should be asked to complete the Week 28 Visit for safety. Patients who have not completed the study as planned (through Week 24) cannot participate in OLE. Patients who (about every 6 to 12months).

Patients that complete the study (defined as completing all visits through Week 24) have the option to enroll into the OLE (See Section 1.4). Patients who complete through Week 24 but decide not to enroll into the OLE, should complete the Week 28 Follow-Up Visit.

⁵ Weight only (no height or BMI) will be performed at Day 1 and Weeks 4, 8, 12, 24, and 28.

weight only (no height of Bivil) will be performed at Day 1 and weeks 4, 6, 12 6 Must have a confirmed diagnosis of PAH in patients' medical history

Background PAH therapy dose regimens must be stabilized for > 12 weeks prior to the screening RHC and on stable dose(s) > 8 weeks prior to the screening RHC to be eligible. All changes and dose adjustments in background PAH therapy must be documented.

Pregnancy tests not required for women who are surgically sterile. FSH required for women with amenorrhea < 2 years at the Screening Visit only to confirm postmenopausal

taken with food. During visits at the clinic or home, all assessments should be done predose, except where otherwise indicated. Patients should bring their IP with them for each IP must be taken daily, morning and evening until the night before the Week 24 visit. Patients must be told not to take a dose the morning of the Week 24 visit. Doses should be visit (including any empty bottles).

10 SAEs will be collected starting at informed consent form signing. AEs will be collected starting at first dosing.

every 4 weeks while on study. Weeks 8, 16 and 20 will be performed at home (with a kit given to the subject by the site) and the results will be confirmed with the subject by a procedures. If a positive result on a urine test, a serum pregnancy test should be completed to confirm. Pregnancy tests will be completed in women of child-bearing potential 11 Serum pregnancy tests will be performed at Screening and urine pregnancy tests over the rest of the study. A negative urine pregnancy test must be completed before Day 1 phone call. Additional pregnancy tests should be completed anytime menstruation is delayed and in women with infrequent or irregular menstrual cycles.

12 Three 12-lead ECGs (at least 1 minute apart) will be collected on Day 1 after at least 5 minutes of rest. Single 12-lead ECGs will be collected at all other time points.

¹³ Coagulation testing will be done at Screening, Weeks 12 and 24.

regimen were not made. If prior approval is obtained from the Sponsor, the screening RHC may be performed on the same day as the randomization procedures, provided that all 14 RHC results from 4 weeks prior to the Screening visit may be used for entry provided the RHC includes all required information and provided that changes to the patient's PAH occur up to 7 days prior to or on the Week 24 Visit. If a patient terminates early, and at or after the Week 12 Visit, an RHC should be performed at the Early Termination Visit. blood draws and other efficacy assessments are conducted prior to the RHC procedure, and the RHC is performed prior to randomization and IP dosing. Week 24 RHC may

15 Echocardiography should be done in supine position after at least 5 minutes of rest.

16 Patients will wear a wrist device for the entire duration of the study, but for endpoint assessments, focus will be on the 3 following periods: Day 1 to Week 4, Week 12 to Week 16, and Week 20 to Week 24. All details of collection will be provided in the study manual.

assessments can be done pre or post dose). At Week 24, no study medication will be taken prior to the clinic visit (the last dose in the Main Study will be the evening before the ¹⁷ Rodatristat Ethyl and Rodatristat PK: At Day 1 and Week 4, a predose PK sample will be collected (patients will take study medication in the clinic). At Week 12, a postdose PK sample will be collected between 1 to 8 hours after the morning dose (patients will take the morning dose in the clinic and the time of dose will be recorded – all other Week 24 visit) and a PK sample will be collected. If the subject enrolls in the OLE, this PK sample will be collected prior to the first dose of study treatment in the OLE. Blood and spot urine samples for 5-HIAA (and urine samples for creatinine) will be collected pre-dose on Day 1 and at Weeks 4, 12, and 24.

¹⁸ Selexipag and ACT-333679 PK (for subjects using selexipag at baseline only): At Day 1 and Week 4, a predose PK sample will be collected (patients will take selexipag in the clinic at these visits, and the PK samples will be collected approximately 12 h after the prior dose) Additional unscheduled safety assessments may be conducted at any time during the study if the Investigator or Sponsor deems it necessary for the safety of the

DocuSign Envelope ID: A0018C3E-C7AD-4578-9E8C-9E8AC2E9E766

Altavant Sciences GmbH Clinical Study Protocol

Protocol RVT-1201-2002 Effective: 19JAN2022

Abbreviations: 5-HIAA = 5-hydroxyindoleacetic acid; 6MWT = 6-minute walk test; AEs = adverse events; BMI = body mass index; BP = blood pressure; C-SSRS = Columbia-Suicide Severity Rating Scale; D = day; ECG = electrocardiogram; ET = early termination; FSH = follicle stimulating hormone; FU = follow up; HADS = Hospital Anxiety and Depression Scale; HR = heart rate; IP = investigational product; IRT = interactive response technology; LFTs = liver function tests; mo = months; NT-proBNP = N-terminal pro-brain natriuretic peptide; OLE = Open-Label Extension; PAH = pulmonary arterial hypertension; PAH-SYMPACT = Pulmonary Arterial Hypertension Symptoms and Impact Questionnaire; QIDS-C = Quick Inventory of Depressive System-Clinician Rated; RHC = right heart catheterization; RR = respiratory rate; SAE = serious adverse event; temp = temperature; WHO FC = World Health Organization Functional Class; Wk = week

DocuSign Envelope ID: A0018C3E-C7AD-4578-9E8C-9E8AC2E9E766

Altavant Sciences GmbH Clinical Study Protocol

Protocol RVT-1201-2002 Effective: 19JAN2022

Schedule of Assessments - Open-Label Extension - (First 24 weeks of Open-Label Extension) 1.4

Study Week ¹ (following Week 24 in Main Study)	D1 Clinic (Week 24 Main Study)	Wk 2 (D14) Telemed/ Phone Call	Wk 4(D28) Clinic	Wk 8 (D56) Clinic or Home	Wk 12 (D84) Clinic	Wk 18 (D126) Clinic or Home	Wk 24 (D168) Clinic	ET ² Clinic or Home
Screening/ Demography/ Baseline								
Informed Consent	X							
Inclusion/Exclusion Criteria	X							
Weight			X ₃	X^3	X ₃		X ₃	X ₃
Treatment								
Concomitant Medications	X	X	X	X	X	X	X	X
Re-Randomization in IRT	X							
Dispensing IP via IRT	X		X		X			
Administer Rodatristat Ethyl	X	X	×	×	×	×	×	
Morning Dose Taken in Clinic with Food ⁴	X		X					
Investigational Product Compliance/ Accountability			X		X	X	X	X
Safety/Tolerability Assessments								
Adverse Events				\	↑ × -			
Pregnancy Test (Serum/urine) ⁵			X	X	X		×	X
Physical Examination			×		×		×	
Vital Signs (BP, HR, RR, temp, oxygen saturation)			X	X	X	X	X	X
12-Lead ECG ⁶			X	X	X	X	X	X
Laboratory – Hematology, Coagulation?, Chemistry, urinalysis,			X	X	X	X	X	X
Columbia-Suicide Severity Rating Scale (C-SSRS)			X		X	X	X	X
Hospital Anxiety and Depression Scale (HADS)			X		X	X	X	X
Quick Inventory of Depressive Symptoms (QIDS-C)			X		X	X	X	X

Clinical Study Protocol Altavant Sciences GmbH

Study Week ¹ (following Week 24 in Main Study)	D1 Clinic	Wk 2 (D14) Telemed/	Wk 4(D28) Clinic	Wk 8 (D56) Clinic or	Wk 12 (D84) Clinic	Wk 18 (D126)	Wk 24 (D168)	ET ² Clinic or Home
	(Week 24	Phone Call		Home		Clinic or	Clinic	
	Main Study)					Home		
Efficacy-Related Assessments								
LMM9			X		X		X	
Right Heart Catheterization (RHC) ⁸							X	X
Echocardiography ⁹					X		X	
WHO FC			X		X		X	
Plasma NT-proBNP level			X		X		X	
PAH Symptoms and Impact Questionnaire (PAH-SYMPACT)					X		X	
Selexipag PK Sampling ¹⁰	X		X					
	a series a series a							

Visits at Week 2 (Telemed/Phone Call) and Week 4 (clinic visit) can occur within +/-2 days from the randomization date; Visits at Weeks 8 (Telemed/Phone call), 12 (clinic),

18 (clinic or home visit), 24 and 28/Follow Up (clinic) can occur within +/-5 days from the randomization date.

Patients who withdraw consent should be asked to complete the ET Visit for safety. Patients who withdraw consent will continue to be followed for vital status from public records such as government vital statistics or obituaries, as allowed by local law, or periodic contact (about every 6 to 12months).

Weight only (no height or BMI) will be performed at Weeks 4, 8, 12, 24, and 28.

⁴ IP must be taken daily, morning and evening. Doses should be taken with food. During visits at the clinic or home, all assessments should be done predose, except where otherwise indicated. Patients should bring their IP with them for each visit (including any empty bottles).

Pregnancy tests not required for women who are surgically sterile. Pregnancy tests will be completed in women of child-bearing potential every 4 weeks while on study. Weeks 8, 16 and 20 will be performed at home (with a kit given to the subject by the site) and the results will be confirmed with the subject by a phone call. Additional pregnancy tests should be completed anytime menstruation is delayed and in women with infrequent or irregular menstrual cycles.

Single 12-lead ECGs will be collected at all time points.

⁷Coagulation testing will be done at Weeks 12 and 24.

8 Week 24 RHC may occur up to 7 days prior to or on the Week 24 Visit. If a patient terminates early, and at or after the Week 12 Visit, an RHC should be performed at the Early Termination Visit.

⁹ Echocardiography should be done in supine position after at least 5 minutes of rest.

10 Selexipag and ACT-333679 PK (for subjects using selexipag at baseline only): At Day 1 and Week 4, a predose PK sample will be collected (patients will take selexipag in the clinic at these visits, and the PK samples will be collected approximately 12 h after the prior dose) Additional unscheduled safety assessments may be conducted at any time during the study if the Investigator or Sponsor deems it necessary for the safety of the

Clinical Study Protocol Altavant Sciences GmbH

HADS = Hospital Anxiety and Depression Scale; HR = heart rate; IP = investigational product; IRT = interactive response technology; LFTs = liver function tests; mo = months; NT-proBNP = N-terminal pro-brain natriuretic peptide; OLE = Open-Label Extension; PAH = pulmonary arterial hypertension; PAH-SYMPACT = Pulmonary Arterial Hypertension Symptoms and Impact Questionnaire; QIDS-C = Quick Inventory of Depressive System-Clinician Rated; RHC = right heart catheterization; RR = respiratory rate; Abbreviations: 5-HIAA = 5-hydroxyindoleacetic acid; 6MWT = 6-minute walk test; AEs = adverse events; BMI = body mass index; BP = blood pressure; C-SSRS = Columbia-Suicide Severity Rating Scale; D = day; ECG = electrocardiogram; ET = early termination; FSH = follicle stimulating hormone; FU = follow up; SAE = serious adverse event; temp = temperature; WHO FC = World Health Organization Functional Class; Wk = week

Schedule of Assessments – Open-Label Extension – (Post 24 Weeks of the Open-Label Extension) 1.5.

	Pregnancy Test	Clinic Visits ⁴	Follow Up ⁴
			(T weeks after last uest of
Week	Every 4 Weeks (+/- 2 days)	Every 24 Weeks (+/- 4 days)	
IP Dispensing via IRT ¹		X	
IP Compliance/ Accountability ²		X	
Concomitant medications	X	X	
Vital Signs (BP, HR, RR, temp, oxygen saturation)		X	X
Pregnancy Test (serum/urine) ³	X	X	X
Laboratory - Hematology, Coagulation, Chemistry (including LFTs)		X	X
Adverse Events	X	X	X

¹ As necessary, 6-month supply of IP will be dispensed.

Additional unscheduled safety assessments may be conducted at any time during the study if the Investigator or Sponsor deems it necessary for the safety of the

² Patients should be instructed to bring their used, partial, and unused IP containers with them to every Clinic Visit to assess compliance and IP accountability.

³ Pregnancy test will be required every 4 weeks, in women of childbearing potential only. Urine pregnancy kits will be provided to the patient. Completion of the pregnancy test, and collection of adverse events and concomitant medications will be documented via telephone contact. Serum pregnancy test to be done to confirm a positive urine test. Additional pregnancy tests should be completed anytime menstruation is delayed and in women with infrequent or irregular menstrual cycles.

⁴ If a patient discontinues IP for any reason a follow-up visit must be performed 4 weeks after the last dose of ID.

Abbreviations: BP = blood pressure; HR = heart rate; IP = investigational product; RT = interactive response technology; LFTs = liver function tests; RR = respiratory rate; temp = temperature

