9. STUDY ASSESSMENTS AND PROCEDURES

Study procedures and their timing are summarized in the SoA in Section 1.3 for the Main Study and in Section 1.4 and Section 1.5 for the OLE.

Safety concerns should be discussed with the Sponsor immediately upon occurrence or awareness to determine if the patient should continue or discontinue IP.

Adherence to the study design requirements, including those specified in the SoA, is essential and required for study conduct.

All screening evaluations must be completed and reviewed to confirm that potential patients meet all eligibility criteria. The Investigator will maintain a screening log to record details of all patients screened and to confirm eligibility or record reasons for screening failure, as applicable.

Once all screening procedures are complete and the Investigator determines that the patient is eligible, the site must upload/send the required supporting documentation for approval by the Sponsor. The required information will include the RHC report (including tracings), PFTs obtained (may use PFTs completed in the 24 week period prior to screening or obtained at Screening), the screening echocardiogram, as well as specific information about the patient's medical history and disease state to further ensure the appropriateness of each patient being enrolled into this study. Approval from the Sponsor must be obtained prior to randomization.

All assessments should be completed predose unless otherwise stated.

If assessments are scheduled for the same nominal time, then the assessments should occur in the following order whenever possible: ECGs, vital signs, safety blood draws, PK blood draws.

Note: The timing of the assessments should allow the blood draw to occur as close as possible to the nominal time but before dosing.

Repeat or unscheduled samples may be taken for safety reasons or due to technical issues with the initial samples.

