9.2.4. Electrocardiograms

Three 12-lead ECGs, one minute apart, will be obtained after at least 5 minutes of rest at Baseline. Single 12-lead ECGs will be performed at all other time points.

Each ECG performed during the study will be obtained using an ECG machine that automatically calculates the HR and measures PR, QRS, QT and QTcF intervals.

The corrected QT interval (QTc) using Fridericia's formula (QTcF) will be used for each individual patient to determine study eligibility and for all on-study ECGs. The QTcF interval will be based on the ECG machine's algorithm.

Clinically significant ECG findings that are present prior to initiation of IP, if not exclusionary, must be documented in the Medical History section of the eCRF. Any clinically significant abnormality that represents a change from baseline will be reported as an AE and followed until resolution.

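### None of the five on-treatment Main Study ECGs has to be post-dose, so a fully compliant site may record QTcF only at or near trough

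*Protocol*

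**What the plan says.** Protocol Section 1.3 (Schedule of Assessments, Main Study) marks a 12-lead ECG at Weeks 4, 8, 12, 18 and 24, besides Screening, Day 1 and follow-up.

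- **Default timing.** Footnote 9: "During visits at the clinic or home, all assessments should be done predose, except where otherwise indicated". Section 9 repeats it: "All assessments should be completed predose unless otherwise stated".
- **ECG texts.** Footnote 12 asks for a triplicate on Day 1 and then says "Single 12-lead ECGs will be collected at all other time points". Section 9.2.4 says "Single 12-lead ECGs will be performed at all other time points". Neither gives a time relative to dose.
- **Week 12.** Footnote 17 says that "patients will take the morning dose in the clinic and the time of dose will be recorded" and that the PK "sample will be collected between 1 to 8 hours after the morning dose". The post-dose requirement covers the PK sample only.
- **Other Week 12 assessments, then Week 24.** The same footnote: "assessments can be done pre or post dose). At Week 24, no study medication will be taken prior to the clinic visit".
- **Why QT is monitored.** Section 2.3 refers to a potential QTc risk described in the Investigator's Brochure, defers its definitive evaluation to a later thorough QT study, and until then treats QT-related arrhythmia as a potential adverse event of special interest. SAP Table 12 lists it at any grade.
- **What the readings decide.** Section 8.1 requires withdrawal on any of three confirmed criteria: QTcF above 500 ms; above 480 ms with a rise from baseline of at least 60 ms; or above 480 ms with a listed clinical event. SAP Section 8.5 tabulates each patient's maximum post-baseline QTcF.

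**The concern.** If a drug's effect on QT follows its concentration, the reading that shows it best is one taken near peak. Here the stopping criteria and the maximum-QTcF table could rest entirely on ECGs taken before the morning dose or on a morning with no dose. A site would break no rule by never recording an ECG in the hours after dosing. Any concentration-related prolongation could then be under-read, and patients could be judged against the Section 8.1 thresholds without a scheduled reading near their highest exposure.

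The setting adds some weight. According to Sections 4.7 and 9.4, earlier repeat dosing was in healthy subjects for up to 14 days, with no previous experience in patients with PAH. This trial doses patients for 24 weeks.

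**Working it through.** The plan states no figure on this point, so there is none to reproduce. The check is a count, followed by an illustration of scale.

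**1. Count of required timings**

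| Visit | Governing text | Required timing |
|---|---|---|
| Week 4 | Footnote 9, Section 9 | Predose by default |
| Week 8 | Footnote 9, Section 9 | Predose by default |
| Week 12 | Footnote 17 | Either |
| Week 18 | Footnote 9, Section 9 | Predose by default |
| Week 24 | Footnotes 9 and 17 | No morning dose taken |

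Predose by default 3, either 1, no morning dose 1; 3 + 1 + 1 = 5. Required post-dose: 0 of 5.

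The ordering rule in Section 9 does not change this. For assessments at the same nominal time, "the assessments should occur in the following order whenever possible: ECGs, vital signs, safety blood draws, PK blood draws". It ranks tasks that share a time; it does not attach the Week 12 ECG to the post-dose PK sample.

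**2. How far trough lies below peak (illustration only)**

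Inputs: single-dose half-lives of about 5 h (rodatristat ethyl) and 12 h (rodatristat), Section 2.1; dosing about every 12 h, Section 6.2. Tmax is not in the documents and is assumed to be 1 to 4 h.

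Simple decay over one interval, 0.5^(12 / half-life):
- rodatristat ethyl: 0.5^(12/5) = 0.19
- rodatristat: 0.5^(12/12) = 0.50

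One-compartment oral model at steady state, with k = ln 2 / half-life and ka chosen so that ln(ka/k)/(ka − k) equals the assumed Tmax:

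C(t) ∝ e^(−kt)/(1 − e^(−12k)) − e^(−ka·t)/(1 − e^(−12ka))

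| Assumed Tmax (h) | Peak/trough, rodatristat ethyl | Peak/trough, rodatristat |
|---|---|---|
| 1 | 4.44 | 1.88 |
| 2 | 3.65 | 1.76 |
| 3 | 2.91 | 1.65 |
| 4 | 2.30 | 1.55 |

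Inverting, trough is 1/1.88 = 53% to 1/1.55 = 65% of peak for the active moiety, and 1/4.44 = 23% to 1/2.30 = 43% for the prodrug. The count in step 1 does not depend on these figures.

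**3. What moving the Week 12 ECG would achieve**

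Required post-dose ECGs rise from 0 of 5 to 1 of 5. Section 2.1 puts steady state at Day 5 and the schedule puts Week 12 at Day 84, so the assured post-dose reading comes 84 − 5 = 79 days after steady state. With the ±5-day window the range is 79 − 5 = 74 to 89 − 5 = 84 days.

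Of the three QTcF criteria in Section 8.1, one uses baseline, and it also needs QTcF above 480 ms.

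**The case against.** The strongest reply is that this is safety monitoring and was never meant to characterise QT. Section 2.3 assigns that to a thorough QT study. Around the scheduled ECGs stand QTcF and long-QT exclusions, a ban on drugs with a known Torsades risk, unscheduled assessments, IDMC review, and a withdrawal criterion linked to syncope, arrhythmia, cardiac arrest or seizure. This stands as a reason for modest priority. It does not fill the gap: the exclusions detect nothing, unscheduled ECGs need a prompt, and the IDMC sees only what is collected.

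A reader might infer that the schedule is hiding QT prolongation or leaving patients exposed to a known hazard. The documents do not support that. Section 4.7 reports no safety concern beyond gastrointestinal events and mild transient ALT elevations, at single doses up to 2000 mg and 800 mg BID for 14 days. Section 6.6.1 reports no clinically significant ECG change in a study using 600 mg BID at steady state. ECG timing in those studies is not given and the Investigator's Brochure is not available here, so this is not proof of safety either.

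A reader might also take predose to mean drug-free. It does not: with a 12 h half-life and 12-hourly dosing, rodatristat at trough is still at roughly half of peak or more.

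Nor are post-dose ECGs forbidden. Footnote 17 permits one at Week 12, and the predose rule is a recommendation, so actual timing may vary.

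Finally, a post-dose Week 12 reading differs from the other visits and from the pre-treatment baseline (SAP Section 4.7.2). That is a real cost. In group summaries it applies equally to placebo, so the concurrent arm largely absorbs it. For an individual patient it bears only on the one baseline-dependent criterion.

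**Conclusion.** The point holds as a gap in monitoring sensitivity: 0 of 5 on-treatment Main Study ECGs must be post-dose, and a compliant site may record QTcF only at or near trough, while QT-related arrhythmia remains a potential event of special interest and withdrawal on confirmed criteria is mandatory.

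The count follows from the text alone. Any under-reading is of unknown size and arises only if QT follows concentration, which the documents do not show. The peak-to-trough ratios rest on an assumed Tmax and a simple model, and serve only for scale.

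Priority is optional to moderate. The case for acting rests mainly on how little the change costs.

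**What to change.** In Section 1.3, footnotes 12 and 17, and in Section 9.2.4, require the already scheduled Week 12 ECG after the in-clinic morning dose, within the existing 1 to 8 h PK window and immediately before the post-dose PK sample, with dose and ECG times recorded. If the sponsor knows Tmax, narrow the window to it. This fits the ECG-before-PK order in Section 9 and pairs QTcF with a concentration.

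Mark Week 12 in the schedule row for the morning dose taken in clinic. That row now marks only Day 1 and Week 4, although footnote 17 has the Week 12 dose taken in clinic.

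Leave the other four ECGs and the Section 8.1 criteria unchanged. No extra confirmation step for a 60 ms rise is needed: Section 8.1 already asks for confirmed criteria and pairs that rise with QTcF above 480 ms.

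**Cost.** Wording changes and one table mark, with no added visit or scheduled test. The Week 12 visit may run longer, within the existing 8 h limit. Week 12 change from baseline becomes a post-dose, fed reading against a pre-treatment baseline, to be read against placebo. The weeks before Week 12 remain without an assured post-dose ECG.
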